Safety Endpoints	
Defined as one or more of the following events occurring within 7 days (168 hours) of the enrollment PE imaging study:
 
 1) Time to treatment of PE > 8 hours defined as the time from study enrollment until initiation of anticoagulant therapy for PE. 2) Complications of PE imaging defined as one or more of the following occurring within 24 hours of the enrollment imaging study and requiring medical or surgical intervention: hypotension, difficulty breathing, acute pulmonary edema or hypervolemia, oral swelling, rash or puritis, abdominal pain, nausea or vomiting, altered mental status, or soft tissue contrast media or radio-isotope extravasation.

	
3) Severe health outcomes defined as one or more of the following occurring within 168 hours of the enrollment imaging study: AKI (Acute Kidney Injury Network [AKIN] 1-3); Death (any cause), renal failure, or one or more of the following requiring medical or surgical intervention: acute myocardial infarction, stroke and/or other acute arterial vascular event, in any anatomic distribution, requiring medical or surgical intervention; death with renal injury as a significant contributor defined as obvious evidence of renal failure defined by worsening azotemia with complications of renal failure including oliguria, pulmonary edema, hyperkalemia, pericardial effusion, or the need to initiate renal replacement therapy before death; identification of a venous thromboembolism (VTE, PE and/or DVT) requiring medical or surgical intervention; death from VTE and/or hemorrhage requiring medical or surgical intervention as a result of treatment for VTE.

Tertiary End-points	Mid- (occurring within 30 days) and Long-term (occurring within 1 year) severe health outcomes
Number of Subjects	
 • A total of 700 subjects will be enrolled inclusive of 600 subjects that will be randomized to CTPA or VQ imaging and 100 non-randomized subjects that will undergo CTPA.
Inclusion Criteria	
 1) Age ≥ 18 years CTPA ordered by the treating provider to evaluate PE. 2) Pre-test probability of PE $\leq 20\%$ defined using the PE Pretest Consult Score. 3) For randomization to CTPA or VQ imaging (600 subjects): AKI risk $\geq 20\%$ assessed by an AKIrisk Score ≥ 2 points 1) For non-randomized CTPA group (100 subjects): AKI risk $< 10\%$ assessed by an AKIrisk Score < 2 points.

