2.2 Secondary objectives

The secondary objectives of this study are to:

- 1) Validate the AKIRisk score, alone and in combination with acute-phase markers of renal dysfunction (Cystatin-C and/or NGAL), to inform imaging strategies and reduce the risk of AKI.
- 2) Compare the incidence of short, mid- and long-term AKI and subsequent health outcomes in patients exposed to iodinated contrast media and unexposed controls at 30-days and at 1-year.
- 3) Measure the 30-day and 1-year incidence of VTE and subsequent severe health outcomes including outcomes related to VTE and VTE treatment.

All secondary outcomes will be defined using composite outcomes and will be determined to be present or absent by the agreement of 2 of 3 blinded physician reviewers, using methods of adjudication successfully employed by the PI in comparable studies.^{7,11,20,46,53,59} Briefly, physician reviewers will be provided with copies of the EMR and patient interview responses. Identifying information will be redacted, and, while the reviewer will have access to any creatinine values recorded in the EMR, they will not be provided with creatinine measurements performed for the study and not recorded in the EMR, nor will they be informed of the subject's status with regard to the primary outcome. Each reviewer will be asked to define each secondary outcome as present or absent, without knowledge of the other reviewers' determinations. In the event of a disagreement between the first and second reviewer, the determination of a third reviewer will be used to define the outcome. No reviewer will be made aware of their designation as the first, second or third reviewer.

Acute Kidney injury will be reported using defined using the Acute Kidney Injury Network (AKIN) definitions (stages 1-3).⁹⁰ KDIGO guidelines do recommends a more standard definition of AKI than for CIN.³⁸ While we do agree with this recommendation, in principle, we are planning a study aimed at changing imaging practices of physicians in specialties that are not as familiar with the. We do plan to measure and report AKIN 1-3 outcomes. We also plan the enrollment of a heterogeneous cohort of patients with renal function ranging from normal to significantly impaired and patients with a range of acute and chronic illnesses of varying severity, consistent with patients treated in the emergency care setting.

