Severe Health Outcomes will be defined for each follow-up period (24 hours, 2-7 days, 30 days, and 1 year) as the combined outcome of death from any cause, renal failure, acute myocardial infarction, stroke, and/or one or more symptomatic complications of arterial-vascular disease, in any distribution, (cerebral, coronary, mesenteric, renal or peripheral) requiring surgical or medical therapy.²⁸ Renal failure will be defined by the AKIN 3 criteria: an increase in creatinine 3 times baseline, or a decrease in eGFR_{Scr} $\geq 75\%$, or an absolute increase in creatinine to ≥ 4.0 mg/dL as a result of an increase of at least 0.5 mg/dL, or the need for renal replacement therapy.⁹⁰ The highest recorded creatinine recorded in the EMR during the follow-up period will be used to determine this outcome. Myocardial infarction will be defined as a cardiac catheterization, autopsy or cardiac imaging study demonstrating acute coronary thrombus or non-viable myocardium; or at least one measured troponin I above the 99th percentile and clinical findings consistent with ischemia; or diagnostic ECG findings including acute ST-T changes, new left bundle branch block, or new pathologic Q-waves.^{96,97} Stroke will be defined as an acute, focal neurologic deficit with symptoms lasting longer than 24 hours and/or imaging or autopsy evidence of acute cerebral infarction. Finally, coronary or cerebrovascular events not meeting the criteria for acute myocardial infarction or stroke, including acute coronary syndromes and transient ischemic attack (TIA), are included within the definition of other arterial vascular events if these events required medical or surgical invention. The PI has successfully applied the same methods of outcome determination in a comparable study.^{7,11,20}

Outcomes involving death will be classified by adjudicators as: 1) Renal injury as a significant contributor defined as obvious evidence of renal failure defined by worsening azotemia with complications of renal failure including oliguria, pulmonary edema, hyperkalemia, pericardial effusion, or the need to initiate renal replacement therapy before death; 2) Death from VTE and/or hemorrhage requiring intervention following anticoagulant treatment for VTE; or 3) Unrelated to VTE or Renal injury. Death outcomes 1) and 2) may be identified concurrently.

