Telephone and Medical Record Follow-up The methods planned for follow-up were developed in part by the PI and her co-investigator ([name]), have been previously published,⁸⁹ and successfully used to complete follow-up for a study of CIN incidence and subsequent outcomes.^{7,11,20,53} The methods planned for follow-up were developed in part by the PI and her co-investigator ([name]), have been previously published,⁸⁹ and successfully used to complete follow-up for a study of CIN incidence and subsequent outcomes.^{7,11,20,53} Follow-up interview will also occur during the 2-7 day follow-up appointment. For patients who did not complete the follow-up visit, we will attempt to contact the patient by telephone and/or email starting at 7-days following enrollment (to identify events occurring within 7 days of enrollment). A review of the EMR will also be performed for outcomes occurring within 24-hours, 7-days, within 30-days and within 1-year. A Social Security Death Index search will be performed for all patients that could not be contacted by telephone or email and for whom survival could not be confirmed by the medical record. In the event of a death, we will attempt to obtain a copy of the death certificate, if available.

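### Renal failure (AKIN 3) is decided from EMR creatinine alone, so an AKIN 3 value seen only on the 2-7 day study draw can be recorded as no renal failure in the adjudicated composite

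*Combined protocol and SAP*

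**What the plan says.** Section 2.2 (Severe Health Outcomes) sets the windows: "Severe Health Outcomes will be defined for each follow-up period (24 hours, 2-7 days, 30 days, and 1 year". Renal failure is one component of that composite: "Renal failure will be defined by the AKIN 3 criteria: an increase in creatinine 3 times baseline". The other AKIN 3 criteria are an eGFR fall of at least 75%, a creatinine of at least 4.0 mg/dL reached through a rise of at least 0.5 mg/dL, or need for renal replacement therapy. The creatinine source is then fixed: "The highest recorded creatinine recorded in the EMR during the follow-up period will be used to determine this outcome".

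The same section gives all secondary outcomes to blinded physician reviewers: "Each reviewer will be asked to define each secondary outcome as present or absent". On study creatinine it says "they will not be provided with creatinine measurements performed for the study and not recorded in the EMR".

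Section 5.1 schedules a follow-up study creatinine between 48 and 168 hours after imaging. It takes the baseline from the enrollment sample when the EMR holds no value within 24 hours of imaging.

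For lesser degrees of kidney injury, section 2.2 says only "We do plan to measure and report AKIN 1-3 outcomes". The précis and section 5.2 list both AKIN 1-3 and renal failure as 7-day safety events. None of these three places names a creatinine source.

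**The concern.** The trial pays for a protocol-driven creatinine because routine care does not supply one. Section 1.4 says that surveillance after contrast exposure is not usual practice, least of all in outpatients, and that data gathered without it understate AKI. For renal failure, section 2.2 then goes back to the routine record. For a patient discharged before 48 hours, the study draw may be the only creatinine in the 2-7 day window.

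At stake is the renal failure component of the adjudicated composite. Section 2.2 (Secondary Outcome Analysis) names renal failure as a dichotomous outcome for logistic regression, with an exact version where events are rare. When events are few, each one left out matters more.

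**Working it through.** The plan states no figure that depends on this rule, so there is nothing to reproduce. The check sets the sections side by side and then asks what can be said about size.

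**Step 1: does the study value reach the renal failure decision?**
- Window: the 2-7 day composite period (section 2.2) is the window of the study draw (section 5.1).
- Source rule: the highest EMR creatinine in the period (section 2.2). No other creatinine source is named.
- Reviewers: they do not receive study values that are absent from the EMR. The wording itself expects that some will be absent.
- Later step: no section enters study results in the EMR, and none applies AKIN 3 to them after adjudication.

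A qualifying value found only on the study draw is therefore outside the rule.

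**Step 2: the baseline.** The threefold criterion needs a denominator. Under section 5.1 this may be a study sample. If that value is not in the EMR, reviewers may be unable to apply the criterion even when the follow-up value is recorded.

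**Step 3: later windows.** The précis lists "Mid- (occurring within 30 days) and Long-term (occurring within 1 year) severe health outcomes", and section 5.1 says "A review of the EMR will also be performed for outcomes occurring within 24-hours, 7-days, within 30-days and within 1-year". Both wordings suggest cumulative windows, but the protocol does not say so outright. If they are cumulative, an AKIN 3 value from days 2-7 belongs in the later composites too. It stays uncounted there only if no later EMR creatinine and no renal replacement therapy qualifies.

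**Step 4: relation to the primary endpoint.** Section 2.1 defines a primary case as a rise of at least 25% or at least 0.5 mg/dL. With baseline b:
- Tripling: (3b − b)/b = 200%, which is at least 25%.
- Reaching 4.0 mg/dL through a rise of at least 0.5 mg/dL meets the 0.5 mg/dL criterion directly.

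So a study value that meets AKIN 3 by either criterion is already a primary-endpoint case. Values hidden on the follow-up draw by these criteria cannot outnumber the primary cases found on study draws that are absent from the EMR. The eGFR criterion was not checked this way because the protocol does not print the equation.

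**Step 5: order of magnitude, illustration only.** Section 4.1 reports about 65% of patients admitted, and section 2.1 plans for 30% dropout. Non-admitted randomized patients: 600 × (1 − 0.65) = 210. With a study draw, if dropout means no draw: 210 × 0.70 = 147. Let r be the AKIN 3 rate and m the share of study values absent from the EMR. The protocol gives neither, so both are assumed. Missed events = 147 × r × m:

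| r | m = 0 | m = 0.5 | m = 1 |
|---|---|---|---|
| 1% | 0 | 0.7 | 1.5 |
| 2% | 0 | 1.5 | 2.9 |
| 3% | 0 | 2.2 | 4.4 |

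This assumes the same r in admitted and non-admitted patients, and it applies an admission share for all CTPA patients to a higher-risk subset. It leaves out inpatients discharged before 48 hours, so it is not an upper bound.

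**The case against.** The strongest defense is that the rule is deliberate. It keeps reviewers blind to the primary outcome, applies one source to all windows, and follows methods that the protocol says were used in a comparable study. Blinding is a good reason to withhold study creatinine where judgment is needed, as for myocardial infarction, stroke or cause of death. The creatinine and eGFR criteria of AKIN 3 are arithmetic and can be applied without a reviewer, so blinding does not require that the study value be ignored.

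Other routes to detection exist. Renal replacement therapy counts whatever the creatinine. Section 1.6 places the study draw in ordinary care facilities, so some results may reach the EMR. Section 6.0 notifies patients who meet the CIN definition, and its letter directs them to care, which may produce an EMR creatinine. These routes narrow the gap, especially for the later windows, but none ensures an EMR value within days 2-7.

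Four stronger readings are tempting, and the documents do not support them:
- *The trial loses these renal failure events altogether.* The 7-day safety endpoint lists renal failure and AKIN 1-3, and section 5.2 has the study manager monitor it. The reviewers' restriction is not stated to apply there, so safety reporting may already use study values.
- *AKIN 1-3 is EMR-only.* Its source is unstated, which makes it unclear, not wrong.
- *Patients with no creatinine are coded as free of renal failure.* Reviewers are offered only present or absent, but the protocol does not say how they rate such a patient. A patient without a draw has no study value to hide, so this is a separate question.
- *The 2-7 day composite is certainly a compared endpoint.* Section 3.3 has secondary outcomes assessed from 30 days, while section 2.2 and the section 5.3 schedule include days 2-7. That timing conflict is also separate.

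**Conclusion.** The point holds for the creatinine and eGFR criteria of renal failure in the adjudicated Severe Health Outcomes composite. If the protocol is followed as written, a value that the trial itself measured and that meets its own AKIN 3 definition can be recorded as no renal failure. This applies to the 2-7 day composite. It extends to 30 days and 1 year only under the two conditions in step 3.

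The size is unknown, because the protocol gives neither an AKIN 3 rate nor the share of study values that reach the EMR. It is probably small: a missed event needs an attended draw, AKIN 3 on that draw or against a study-only baseline, no qualifying EMR evidence and no renal replacement therapy. The step 5 figures are illustrations under assumed inputs.

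The primary endpoint uses the study draw and is unaffected. A reader might infer bias between CTPA and VQ, but both arms have the same draw, source rule and reviewers, and nothing in the documents shows a difference. The concern is under-counting of a secondary component, and it is worth correcting because the data are already in hand.

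**What to change.** 1. Amend the source sentence in section 2.2. Derive the creatinine and eGFR criteria of AKIN 3 by program, outside adjudication, from the highest of all study and EMR creatinine values in the period. Use the section 5.1 baseline, whether EMR or study sample. Combine the result with the adjudicated components.
2. Keep reviewers blind to study creatinine and to primary-outcome status.
3. State the same creatinine source for AKIN 1-3 and renal failure in the précis, section 2.2 and section 5.2.
4. Say whether the 30-day and 1-year composites are cumulative. If they are, carry the 2-7 day study value into them.
5. State that a patient with any qualifying component (death, renal replacement therapy, myocardial infarction, stroke or another arterial event) stays an event whether or not a creatinine is available. A blanket rule setting patients without creatinine to missing would discard known events and should not be used.
6. Report, by arm, the AKIN 3 cases found only on study values.

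The cost is protocol and SAP wording plus a short program on values already collected. It needs no new samples, visits or reviewers.

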Venous Thromboembolism (VTE) including PE and/or DVT will be defined by the identification of one or more thrombus, requiring medical or surgical intervention, in the deep veins of the extremities or in the pulmonary vasculature as determined by ultrasonography, echocardiography, CT, MRI, VQ or on autopsy. We will also record and report severe outcomes secondary to VTE and treatment of VTE, including hemorrhage from anticoagulant treatment.

Complications of PE imaging will be defined for the first 24 hours after imaging, patients will be followed for one or more of the following recorded in the EMR, and requiring medical or surgical intervention: hypotension defined as a SBP ≤90 mmHg or ≥10% below baseline, dyspnea, acute pulmonary edema or hypervolemia, oral swelling, rash or puritis, abdominal pain, nausea or vomiting, altered mental status, or soft tissue contrast media or radio-isotope extravasation. The PI has previously published these methods of outcome determination.⁵³

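### Deaths of undetermined cause have no class of their own, so they will tend to be adjudicated as unrelated to VTE or renal injury

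*Combined protocol and SAP*

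**What the plan says.** The last paragraph on outcome definitions in section 2.2 (Secondary objectives) begins "Outcomes involving death will be classified by adjudicators as" and gives three classes.

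- The first is "Renal injury as a significant contributor defined as obvious evidence of renal failure defined by worsening azotemia", together with listed complications of renal failure or the need to start renal replacement before death.
- The second is "Death from VTE and/or hemorrhage requiring intervention following anticoagulant treatment for VTE".
- The list closes with "3) Unrelated to VTE or Renal injury. Death outcomes 1) and 2) may be identified concurrently". The first two classes may be combined; the third stands alone.

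The same section sets the adjudication procedure: "Each reviewer will be asked to define each secondary outcome as present or absent", with agreement of two of three blinded physicians. The material listed for them is the electronic medical record and the patient's interview responses. VTE is defined there as a thrombus needing treatment, "in the deep veins of the extremities or in the pulmonary vasculature as determined by ultrasonography, echocardiography, CT, MRI, VQ or on autopsy".

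Section 5.1 (Telephone and Medical Record Follow-up) provides for a death-index search when a patient cannot be contacted and the record does not confirm survival. It adds: "In the event of a death, we will attempt to obtain a copy of the death certificate, if available".

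**The concern.** The third class is a positive statement that VTE and renal injury played no part. A death about which little is known does not support that statement, yet the list offers nowhere else to put it. A fatal PE outside hospital after a negative index scan would leave this kind of sparse record.

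Cause-specific death feeds three things the plan intends to report: the safety comparison of diagnosed and missed VTE between arms, the VTE-death component of the safety endpoints, and the VTE-related outcomes at 30 days and 1 year under secondary objective 3. If undetermined deaths go into the unrelated class, VTE-related and renal-related death are both understated. The reader of the results also cannot tell a documented alternative cause from an absence of information.

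**Working it through.** The documents give no figure for cause-specific death, so there is none to reproduce. The check is to apply the definitions to the kinds of death the protocol foresees.

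**Inputs**

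- Closed list of three classes; only the first two may coexist (section 2.2).
- Class 1 needs obvious evidence of renal failure (section 2.2).
- VTE needs a thrombus on imaging or at autopsy (section 2.2).
- Listed adjudication material is the medical record and interview responses; neither the death certificate nor the death-index result is listed (section 2.2).
- Death index used as a last resort; certificate not assured (section 5.1).

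**Application**

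| Death | Class 1 | Class 2 | Result |
|---|---|---|---|
| In hospital, renal failure documented | met | depends on record | class 1, with or without 2 |
| At home, index scan showed PE | no evidence | thrombus is on record | class 2 supportable |
| At home, index scan negative, no later imaging, autopsy or certificate | no evidence | no thrombus shown | only class 3 is left, unless judgement favours class 2 |
| At home after undocumented renal failure | not obvious | no thrombus shown | only class 3 is left |
| Fatal bleed on anticoagulant before any intervention | no evidence | wording unclear | class 2 or class 3 |

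**Search for a rule elsewhere.** Section 6.2.4 has deaths within 7 days reported with whatever is known about cause. That concerns reporting where the IRB requires it, not classification of the outcome. No section supplies an undetermined level or a rule for insufficient information.

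**Effect on the comparison of arms.** In one arm, let D be fatal PEs that the index test detected and M those it missed. Assume that detected ones are attributed correctly and that a missed one is attributed to VTE with probability q < 1.

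- True PE deaths = D + M
- Recorded PE deaths = D + qM
- Shortfall = (1 − q)M

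The shortfall grows with M, so at equal q it is larger in the arm whose test misses more fatal PE. This shows direction only; the documents give no value for D, M or q.

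**What does not change.** The primary endpoint rests on creatinine. The severe health outcomes composite in section 2.2 counts death from any cause in every follow-up period. The 168-hour safety composite (synopsis and section 5.2) also counts any death. The class assigned cannot alter any of these.

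**The case against.** The best reply is that no sentence equates unknown with unrelated. Class 2 has no attribution criteria of its own, and the imaging-or-autopsy definition is for VTE as an outcome, not for VTE as a cause of death. Physicians could judge PE the probable cause and choose class 2. That stands, and it is why the point is a tendency and not a certainty. But it also means that two equally undocumented deaths may be filed differently, with nothing in the plan to govern the choice.

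It is also fair that exposure is narrow. The death index is searched only after attempts at contact have failed and the record does not confirm survival, and certificates are then sought. That stands too.

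On fatal haemorrhage, a reader might infer that a patient who bleeds to death before treatment must be called unrelated. The text does not compel this. The phrase about intervention can be read as a severity qualifier, and the VTE paragraph of section 2.2 separately promises to report haemorrhage from anticoagulants without that limit. What remains is an ambiguity.

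A reader might also infer that the scheme hides any excess of deaths in the arm that misses more PE. It does not: such deaths still count in all-cause death by arm. What is weakened is the ability to say why they occurred.

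Nor does filing such a death as unrelated contradict the evidence, since by construction there is none. Patients enter with a pre-test PE probability of at most 20%, and age and coronary disease score towards entry to the randomised group. Many undocumented deaths will truly be unrelated.

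**Conclusion.** The gap is real and confined to cause-specific death. As written, the plan will tend to place poorly documented deaths in the unrelated class. It thereby understates VTE-related and renal-related death, and could do so more for missed PE than for detected PE. This rests on two assumptions: that some deaths will reach the adjudicators without imaging, autopsy or other evidence of cause, which section 5.1 anticipates, and that adjudicators follow the stated definitions closely.

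The size cannot be estimated from the documents. A reader might try assumed inputs, such as 1-year mortality of 5–15% and unknown cause in 10–30% of deaths: 300 × 0.05 × 0.10 = 1.5 to 300 × 0.15 × 0.30 = 13.5 deaths per arm. Nothing in the protocol anchors either input, and not every such death would be wrongly classed. Setting that range against the 3% 45-day VTE incidence in section 1.5 (300 × 0.03 = 9 per arm) would mix a 1-year window with a 45-day one and compare deaths with VTEs of any severity. It does not support a claim that misfiled deaths rival the number of true VTE deaths.

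The change is worth making because it is cheap and bears on whether missed fatal PE can be recognised. It does not bear on the primary conclusion.

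**What to change.** 1. Add a fourth class in section 2.2 and on the adjudication form: undetermined, meaning that VTE, treatment-related haemorrhage or renal injury cannot be excluded.
2. Reserve class 3 for deaths with a documented other cause.
3. Include any death certificate and death-index result in the material sent to adjudicators, redacted as the rest is.
4. Report VTE-related death by arm as class 2 alone and as class 2 plus class 4. Do the same for renal death with class 1 alone and class 1 plus class 4.
5. State in section 2.2, section 5.2 and the synopsis safety endpoints that the phrase on intervention does not exclude a haemorrhage that was fatal before intervention. This agrees with the VTE paragraph of section 2.2.

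The cost is a revised form, a few lines of analysis text and one extra tabulation. The downside is small: the wider counts will include some deaths that were not due to VTE or renal injury, which is why both counts should be shown.
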